#### Severe Adverse Events:

Severe Adverse Events (SAE) are internal events and include: death, Life-threatening experience, Hospitalization (for a person not already hospitalized), Prolongation of hospitalization (for a person already hospitalized), Persistent of significant disability or incapacity, Congenital anomaly and/or birth defects, Any event that jeopardizes the subject and may require medical or surgical treatment to prevent one of the preceding outcomes. As the research staff becomes aware of SAE's they will be reported to the Institutional review board. However, since eligibility criteria states a

participant must be pregnant and have gestational diabetes, all participants are expected to be admitted to the hospital to deliver their baby; therefore, this will not be considered an unanticipated event.

## **Compensation**

No monetary compensation will be provided to participants.

## **INCLUSION CRITERIA**

- Gestational diabetes
- Pregnancy > 12 weeks gestation
- 18 years of age or older
- Ability to give consent
- Women with gestational diabetes who fail dietary management of diabetes

## **EXCLUSION CRITERIA**

- Inability to consent to the study
- Pre-existing diabetes
- G6PD deficiency
- Serum creatinine >1
- Liver disease
- Allergy to sulfa
- Allergy to glyburide (Patients will be assessed for any past medical history to include allergies to this medication)
- Allergy to metformin (Patients will be assessed for any past medical history to include allergies to this medication)
- Fetal anomalies
- Women who will not monitor their blood glucose

## **DATA MANAGEMENT**

Consent forms and HIPPA release of information forms will be stored in locked cabinets in the Department of OB/GYN. Participants who wish to withdraw must notify the PI, in which a note will be made to their study file. All data collected on participants who withdraw will be de-identified in the database and will be used in the data analyses.

## **STATISTICAL ANALYSIS**

Data will be analyzed using SAS 9.3 software (SAS Institute, Inc., Cary, North Carolina). The distribution of potential confounders across the two arms of the study will be examined.

### *Sample size calculations*

Sample size calculations were performed using SAS software and OpenEpi (Open Source Epidemiologic Statistics for Public Health, [www.openepi.com](http://www.openepi.com), Version 3.03a). The method of Fleiss with continuity correction was used. The sample size calculation was performed assuming a failure rate associated with glyburide of 31% and the failure rate of glucovance at 10%, to provide an 80% chance of detecting a 5% difference in the rate of failure between the two drugs. Drug failure is defined as 20% of values over two consecutive weeks (i.e. each week 20% of the measured values) fail to meet the glycemic goals of fasting  $\leq 95$ mg/dl and 1 hour postprandial  $\leq 140$ mg/dl. Sixty- seven patients are required in each arm.

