Glucovance is a drug combination of glyburide and metformin (aka glucophage). Both glyburide and metformin have been studied individually in pregnancy and are often used together in pregnancy as separate doses of each drug. The combined drug, glucovance, has not been studied in pregnancy. Glyburide and metformin have complementing mechanisms of action, so patients who take glucovance may have better glycemic control.

Oral antidiabetic drugs have been found suitable for the management of gestational diabetes because of their ability to provide good glycemic control when used properly. It is known that glyburide and metformin do cross the placenta, but there are no recorded long-term studies that have shown the implications of in utero exposure to these drugs.

[figure not shown]
Current literature notes that glyburide has been associated with higher neonatal birth weight, neonatal hypoglycemia, increased macrosomia (Jiang et al., 2015). No studies indicated increased fetal death associated to the use of oral blood sugar medications. Glyburide and Metformin have been studied extensively for use in pregnancy; however there are no published studies on the use of the combination drug glucovance during pregnancy. The failure rate for metformin and glyburide used as single agents is relatively high. The purpose of this study is to see if the combination drug has a lower failure rate. The proposed study will compare glyburide and glucovance in the treatment of gestational diabetes.

**STUDY DESIGN:** A randomized open label study of patients with GDM not controlled with diet.

Patients will be randomized to either glucovance or glyburide. Sixty-Seven patients are required in each arm.

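### The power statement claims 80% power for a 5% difference in drug failure, but 67 per arm is sized for a 21-point difference and has about 7–14% power for 5 points

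*Combined protocol and SAP*

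**What the plan says.** The section on sample size calculations, under Statistical Analysis, names its method: "The method of Fleiss with continuity correction was used". One sentence then gives both the assumed rates, "assuming a failure rate associated with glyburide of 31% and the failure rate of glucovance at 10"%, and the claim that the size is "to provide an 80% chance of detecting a 5% difference in the rate of failure between the two drugs". The section ends with the number, "Sixty- seven patients are required in each arm", and the Study Design paragraph and the abstract give the same figure. Neither alpha nor sidedness is given for the calculation, and no allowance for dropout is described.

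The Data Analysis section plans a chi-square or Fisher's exact test on drug failure, and a risk ratio with a 95% confidence interval.

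**The concern.** The two assumed rates differ by 31 − 10 = 21 points, yet the detectable difference is given as 5%. Required size grows roughly with the inverse square of the difference, so a design sized for 21 points falls far short for 5.

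This matters because drug failure is the only outcome with a power calculation, and the stated purpose of the study is to see whether the combination fails less often. A reader who trusts the sentence could take a non-significant result as evidence that the drugs differ by less than about 5 points. Differences well above 5 points but below 21 are also plausible on the plan's own figures. The Background puts glyburide failure at 16–20%, and at 20% versus 10% the power with 67 per arm is only 29% (Fisher, exact) to 37% (chi-square, exact).

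**Working it through.** **Inputs.** From the sample size section: failure rates 31% and 10%, power 80%, Fleiss with continuity correction, 67 per arm. From the Data Analysis section: chi-square or Fisher's exact test.

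**Assumed.** Alpha is two-sided 0.05, consistent with the planned 95% confidence interval. The plan does not say which two rates would be 5 points apart, so I used pairs tied to its own 31% or 10%: 31% versus 26%, 15% versus 10%, and 10% versus 5%.

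**Formulas.** With d = |p1 − p2|, p̄ the mean of the two rates and q = 1 − p:

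- Uncorrected size: n′ = [1.960·√(2p̄q̄) + 0.842·√(p1q1 + p2q2)]² / d²
- Corrected size: n = (n′/4)·[1 + √(1 + 4/(n′d))]²
- Approximate power: Φ{[d√n − 1.960·√(2p̄q̄)] / √(p1q1 + p2q2)}. For the continuity-corrected version, n is replaced by (n − 1/d)²/n.

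**Step 1: reproduce the plan's 67 (31% versus 10%).**

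- 2p̄q̄ = 2 × 0.205 × 0.795 = 0.32595, and 1.960 × √0.32595 = 1.119
- p1q1 + p2q2 = 0.2139 + 0.0900 = 0.3039, and 0.842 × √0.3039 = 0.464
- n′ = (1.119 + 0.464)² / 0.21² = 2.5057 / 0.0441 = 56.8
- n = (56.8/4) × [1 + √(1 + 4/(56.8 × 0.21))]² = 66.0

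If n′ is first rounded up to 57, the correction gives (57/4) × [1 + √(1 + 4/(57 × 0.21))]² = 66.2, which rounds up to 67. The stated size is therefore reproduced from the 21-point contrast. Other variants do not give it: 57 two-sided uncorrected, 54 one-sided corrected, 45 one-sided uncorrected.

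**Step 2: size needed for 5 points (same method).**

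- 31% versus 26%: n′ = 3.1959 / 0.0025 = 1,278.3; corrected, 1,319 per arm
- 15% versus 10%: n′ = 1.7140 / 0.0025 = 685.6; corrected, 726 per arm
- 10% versus 5%: n′ = 1.0861 / 0.0025 = 434.4; corrected, 474 per arm

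**Step 3: power with 67 per arm (√67 = 8.185).**

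- 31% versus 10%: (0.21 × 8.185 − 1.119) / √0.3039 = 1.088, so 86.2%
- 31% versus 26%: (0.05 × 8.185 − 1.251) / √0.4063 = −1.321, so 9.3%
- 15% versus 10%: (0.05 × 8.185 − 0.917) / √0.2175 = −1.088, so 13.8%
- 10% versus 5%: (0.05 × 8.185 − 0.730) / √0.1375 = −0.865, so 19.3%

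For the corrected column below, (67 − 1/0.21)²/67 = 57.8 replaces 67 at 21 points, and (67 − 20)²/67 = 33.0 replaces it at 5 points. The last two columns enumerate all binomial outcomes.

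| Rates | Normal, uncorrected | Normal, corrected | Exact, chi-square | Exact, Fisher |
|---|---|---|---|---|
| 31% v 10% | 86.2% | 80.7% | 87.3% | 82.7% |
| 31% v 26% | 9.3% | 6.5% | 9.7% | 6.9% |
| 15% v 10% | 13.8% | 8.9% | 13.7% | 9.1% |
| 10% v 5% | 19.3% | 11.6% | 19.5% | 10.6% |

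One-sided 0.05 without correction, the most lenient variant tried, gives 16%, 22% and 29% for the three 5-point pairs.

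**Step 4: what 67 per arm can detect.** With 31% failure on glyburide, the difference detectable with 80% power is 20.9 points by Fleiss with correction, or 19.4 points by exact chi-square.

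**The case against.** The best defence is that this is a drafting slip. Both rates are printed beside the wrong figure, so a careful reader can see the true contrast. The 5% may be the significance level in the wrong place, which would also explain why no alpha appears. The sample size, the test and the definition of failure do not depend on the phrase. The Data Analysis section also requires a confidence interval, which would show how wide a range of effects remains open, so misreading a null result is a risk and not a certainty.

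Much of that stands. The number of patients is not in question, and the interval is a real safeguard. But the sentence is the plan's only statement of power, and it expresses the 5% in words as a difference in failure rates between the drugs. If alpha was meant, the plan still states no significance level correctly, and sidedness is missing on either reading.

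It is also fair to object that 7–14% is not a bound. It depends on the pairs chosen, and at 10% versus 5% power reaches about 20%. That widens the range but leaves it far from 80%.

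**Conclusion.** The concern holds: the power statement is wrong as written. The stated 67 per arm comes from a 21-point contrast and has the intended power there (80.7% by the named method, 82.7% by exact Fisher, 87.3% by exact chi-square). For a 5-point difference its power is about 7–14% at 31% versus 26% or 15% versus 10%, and at most about 20% at 10% versus 5%, all at two-sided 0.05.

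The conclusion rests on two assumptions: two-sided alpha of 0.05, supported by the reproduced size and the planned 95% interval, and the choice of 5-point pairs. Changing either one, including a switch to one-sided testing (at most 29%), does not bring power near 80%. That the 5% was meant as alpha is a reasonable guess, but the text does not say so.

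**What to change.** Correct this before the plan is relied on. Replace the power sentence with wording such as:

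> With 67 patients per arm, using the Fleiss method with continuity correction and a two-sided significance level of 0.05, the trial has 80% power to detect a reduction in drug failure from 31% on glyburide to 10% on glucovance (21 percentage points). A non-significant result will not exclude smaller differences.

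Delete the 5% difference claim. The sponsor should confirm the alpha and sidedness actually used before they are written in. The final caution is not needed to remove the contradiction, but it guards against over-reading a null result.

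The cost is a short edit to one section. The stated detectable difference becomes less favourable; the number of patients and the analysis do not change.

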### *Data analysis*

Patient outcomes will be compared between groups. The initial analysis of the dichotomous outcome (oral medication failure) will involve the creation of a 2 x2 contingency table and the use of a chi-square or Fisher's exact test as appropriate. A risk ratio (RR) for the outcome of drug failure comparing the two medications will be calculated from a log-binomial regression models using the GENMOD Procedure. The RR will be reported along with a 95% confidence interval and P value. If confounding is detected then an adjusted RR will be calculated. Additionally, glucose and dietary diaries will be analyzed.

